8.4 Clinical Outcome Assessments (COAs)

Several clinical outcome assessments will be evaluated. These include:

- Graft function as measured by eGFR using the CK-EPI equation,
- Graft survival as determined by presence of a functioning graft that has not required a re-transplant or permanent renal replacement therapy,
- Subject survival,
- Graft rejection based on kidney biopsy results and 2017 Banff Kidney Meeting Report,

- BKV nephropathy: based on kidney biopsy results and the Banff Working Group on Polyomavirus Nephropathy classification system

NOTE: Renal biopsies are not mandated, but if they are performed during the study period, results will be recorded in the eCRF. The assessments are incorporated into endpoints analyzed for efficacy. See [Section 10.5](#), Efficacy Analysis.

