7.3.3 Demographic and Baseline Characteristics

The following demographic and baseline characteristics will be summarized:

- Age (years) and age categories (<65 years vs. ≥ 65 years);
- Sex;
- Race;
- Ethnicity
- Height (cm);
- Weight (kg);
- Body mass index (BMI) (kg/m^2) ;
- eGFR based on the CK-EPI equation ($\text{mL}/\text{min}/1.73\text{m}^2$) and eGFR categories (<15, 15-<30, 30-<60, 60-<90, and ≥ 90);
- Living donor (Yes vs. No);
- Pre-existing BKV nephropathy (Yes);

Note: Pre-existing BKV nephropathy can be identified based on the following CRF data:

- Medical history using the preferred term ‘Polyomavirus-associated nephropathy’; and
- Clinical outcome assessments indicating subjects developed or possibly developed BKV associated nephropathy at Baseline visit.

- Time from kidney transplant (days);

Time from kidney transplant (days) is calculated as the first dose date of study drug - date of kidney transplant;

- Baseline plasma viral load (copies/mL);
- Duration of BK viremia

Duration of BK viremia (days) is calculated as the first dose date of study drug - date of first reported BK plasma positive PCR

Note: the first reported BK plasma positive PCR is based on CRF data of Historical BKV Blood Sample Results and the quantitative result in copies/mL $\geq 10^3$.

- BKV genotype

Demographic and Baseline characteristics will be summarized with descriptive statistics or counts and percentages of subjects as appropriate for the ITT, MITT, and Safety Populations. Other parameters of Kidney donor profile index (KDPI) will be listed.

7.3.4 *Medical History*

Medical history will be coded to system organ class and preferred term using the Medical Dictionary for Regulatory Activities (MedDRA, Version 22.1). Counts and percentages of subjects with medical history by system organ class and preferred term will be summarized by treatment based on the ITT, MITT and Safety Populations.

All medical history will be listed by treatment and subject.

7.3.5 *Concomitant Medications*

Prior and Concomitant medications will be coded to anatomical therapeutic chemical (ATC) class and preferred term using the World Health Organization (WHO) Drug Dictionary (September 2019G B3).

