7.5.1.7 Rate of Decrease in BKV Plasma Viral Load by Visit

Rate of decrease in BKV plasma viral load is calculated using the following formula:

Rate of decrease = Change from baseline (copies/mL) / time (weeks) between baseline and post-baseline.

The BKV plasma viral load at 1 week, 2 weeks, 4 weeks, 8 weeks, 12 weeks, 16 weeks and 36 weeks with LOCF, change from baseline and rate of decrease will be summarized with descriptive statistics.

Treatment difference in the rate of decrease between each treatment dose group and combined placebo group will be assessed at the specified visit with LOCF using an ANOVA model with treatment (four levels) as a factor. The least squares (LS) mean, SE, 95% CI, and p-value will be obtained from the model estimates. The normality of the residuals from the ANOVA model will be assessed using the Shapiro-Wilk statistic and graphical examination. If data shows significant deviation from normality, the Wilcoxon rank sum test will be applied if necessary.

In addition, the pairwise treatment differences will be analysed using the two-sample t test. The p-value from each t test will be presented.

7.5.1.8 Change in eGFR from Baseline to Week 12, Week 16 and Week 36

eGFR is calculated using the CK-EPI equation. The eGFR at Week 12, Week 16 and Week 36 with LOCF, change from baseline will be summarized with descriptive statistics.

Treatment difference in the eGFR change from baseline between each treatment dose group and combined placebo group will be assessed at Week 12, Week 16 and Week 36 with LOCF using an ANOVA model with treatment (four levels) as a factor. The LS mean, SE, 95% CI, and p-value will be obtained from the model estimates. The normality of the residuals from the ANOVA model will be assessed using the Shapiro-Wilk statistic and graphical examination. If data shows significant deviation from normality, the Wilcoxon rank sum test will be applied if necessary.

In addition, the pairwise treatment differences will be analysed using the two-sample t test. The p-value from t test will be presented.

7.5.1.9 Proportion of Subjects with BKV Nephropathy by Week 12, Week 16 and Week 36

The number and percentage of subjects with BKV nephropathy by Week 12, Week 16 and Week 36 based on renal biopsy, clinical diagnosis or other method of diagnosis as reported in the eCRF

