will be tabulated and summarized by whether BKV nephropathy was confirmed by biopsy or diagnosed clinically in the absence of biopsy results. All instances of biopsies demonstrating BKV nephropathy will be reported in the CSR, however cases of biopsy-proven BKV nephropathy in patients with no pre-study biopsy, stable or improvement serum creatinine and improving BKV plasma viral loads will be excluded from the summary to avoid counting patients who most likely had BKV nephropathy prior to study entry. Exclusion of these patients from the summary will be based on the opinion of the SSRC and documented.

The method of diagnosis during the study reported in eCRF will be summarized at an overall post-baseline visit. If the subjects have different methods of diagnosis reported at different post-baseline visits, the same subject will be counted in the different methods of diagnosis.

The proportion of subjects with BKV nephropathy by Week 12, Week 16 and Week 36 will be analyzed using a logistic regression model with treatment (four levels) as a factor. For the treatment comparison between each treatment dose group and combined placebo group, the estimated odds ratio, 95% CI, and p-value will be presented.

In addition, the pairwise treatment comparisons in the proportion will be made using Fisher's Exact Test. The treatment difference estimates, the exact 95% CI, and p-values from Fisher's Exact Test will be presented.

7.5.1.10 Proportion of Subjects with Graft Failure by Week 12, Week 16 and Week 36

The number and percentage of subjects with graft failure (i.e., permanent requirement for renal replacement therapy) by Week 12, Week 16 and Week 36 will be tabulated.

The proportion of subjects with graft failure by Week 12, Week 16 and Week 36 will be analyzed using a logistic regression model with treatment (four levels) as a factor. For the treatment comparison between each treatment dose group and combined placebo group, the estimated odds ratio, 95% CI, and p-value will be presented.

In addition, the pairwise treatment comparisons in the proportion will be made using Fisher's Exact Test. The treatment difference estimates, the exact 95% CI, and p-values from Fisher's Exact Test will be presented.

7.5.1.11 Proportion of Subjects with Acute Rejection by Week 12, Week 16 and Week 36

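### The tested BKV-nephropathy proportion mixes biopsy-proven with unbiopsied diagnoses and has no new-onset rule, and its one carve-out for prior disease is partial and response-dependent

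*SAP*

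**What the plan says.** **Case definition.** Protocol 8.4 gives "BKV nephropathy: based on kidney biopsy results and the Banff Working Group on Polyomavirus Nephropathy classification system". The same section adds: "Renal biopsies are not mandated, but if they are performed during the study period, results will be recorded in the eCRF". SAP 7.5.1.9 instead counts nephropathy "based on renal biopsy, clinical diagnosis or other method of diagnosis as reported in the eCRF". Protocol Section 10 lets the SAP prevail over the protocol on data analysis, so the wider definition governs.

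**Tabulation and test.** In SAP 7.5.1.9 the counts "will be tabulated and summarized by whether BKV nephropathy was confirmed by biopsy or diagnosed clinically in the absence of biopsy results". The logistic regression (treatment at four levels) and the pairwise Fisher tests are specified for a single overall proportion at Weeks 12, 16 and 36.

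**Pre-existing disease.** SAP 7.3.3 derives pre-existing BKV nephropathy as a baseline characteristic, from medical history and from "Clinical outcome assessments indicating subjects developed or possibly developed BKV associated nephropathy at Baseline visit". Protocol 3.2.2 does not list nephropathy as an exclusion criterion. SAP 7.5.1.9 does not refer to the 7.3.3 variable.

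**Carve-out.** SAP 7.5.1.9 makes one exception, which covers "cases of biopsy-proven BKV nephropathy in patients with no pre-study biopsy, stable or improvement serum creatinine and improving BKV plasma viral loads". On what then happens to them, and for what purpose, the section says that they "will be excluded from the summary to avoid counting patients who most likely had BKV nephropathy prior to study entry". On who decides, it says: "Exclusion of these patients from the summary will be based on the opinion of the SSRC and documented".

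**Change log.** For this endpoint, SAP Section 9 lists only the added time points.

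**The concern.** The protocol's benefit case (Protocol 1.8) rests partly on preventing BKV nephropathy, so a reader will take a lower proportion on MAU868 as disease prevented. That reading needs cases that arose after dosing started and a case definition that the reader can identify. The plan secures neither.

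- Prior disease cannot be prevented. If it is counted equally in all arms it pulls the contrast towards no difference. If it falls unevenly by chance in arms this small, it can look like an effect or hide one.
- A carve-out that operates only when viral load improves is tied to what the drug is meant to do. It could remove more cases from active arms than from placebo.
- A reader holding Protocol 8.4 would assume that the tested cases are biopsy-proven, and nothing in SAP Section 9 corrects that.

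The endpoint, through Week 12, is also in the second interim package (SAP 8.2.2), which the SSRC reviews before Cohort 3 opens.

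**Working it through.** The documents give no rate, effect size or power for this endpoint, so there is no figure of the plan's own to reproduce. The check is mainly textual, with arithmetic for size.

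**1. Definition, side by side.**

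| | Protocol 8.4 | SAP 7.5.1.9 |
|---|---|---|
| Biopsy-proven, Banff-classified | counts | counts |
| Clinical diagnosis, no biopsy | does not count | counts |
| Other method | does not count | counts |
| Listed in SAP Section 9 | – | no, added weeks only |

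For acute rejection, SAP 7.5.1.11 keeps the protocol's biopsy and Banff basis. Only nephropathy was widened.

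**2. Which prior cases does the carve-out reach?** All of its conditions must hold, and the SSRC must agree.

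| Subject with disease before entry | Reached? |
|---|---|
| Positive on-study biopsy, no pre-study biopsy, creatinine stable or better, viral load improving | yes |
| Same, but viral load not improving | no |
| Same, but creatinine worsening | no |
| Pre-study biopsy available | no |
| Clinical or other diagnosis only | no |

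A subject whose disease was documented by biopsy before entry is therefore not removed by this rule, and no other rule in the SAP removes that subject. The text also leaves open whether exclusion from the summary extends to the tested proportion.

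**3. Who decides, and on what.** Improvement in viral load is a post-randomisation outcome and is itself the subject of the other efficacy endpoints. SAP Sections 5 and 8 have the SSRC review unblinded data at both interim analyses. Nothing in 7.5.1.9 requires the exclusion decision to be blinded or made before those reviews.

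**4. Size of one case.** SAP Section 3 gives 8 MAU868 subjects per cohort and 3 × 4 = 12 pooled placebo.

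- Active arm: 1/8 = 12.5 points.
- Pooled placebo: 1/12 = 8.3 points.

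Two-sided Fisher test at 0.05, 8 against 12:

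- Active 0/8: significance needs at least 6/12 on placebo (p = 0.042; 5/12 gives p = 0.055).
- Active 1/8: significance needs at least 8/12 (p = 0.028; 7/12 gives p = 0.070).

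One active-arm case counted or removed thus shifts the placebo count needed from 6 to 8 or back. If the excluded subject also leaves the denominator (0/7), the requirement is still 6/12 (p = 0.044).

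**5. Dilution if baseline cases are counted (illustration).** Let q be the share with baseline disease and p the new-onset risk. Then observed risk = q + (1 − q)p. Assumptions: placebo p = 3/11 = 27% or 5/11 = 45%, from the 3–5% nephropathy and about 11% viremia in Protocol 1.1; a true risk ratio of 0.25; q of 10% to 30%. None of these is a trial estimate.

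Worked case, p = 3/11 and q = 0.10:

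- Active: 0.10 + 0.90 × 0.068 = 0.161
- Placebo: 0.10 + 0.90 × 0.273 = 0.345
- Ratio: 0.47

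| q | Ratio (Fisher power), p = 27% | Ratio (Fisher power), p = 45% |
|---|---|---|
| 0 | 0.25 (5%) | 0.25 (23%) |
| 10% | 0.47 (6%) | 0.40 (18%) |
| 20% | 0.61 (6%) | 0.52 (14%) |
| 30% | 0.71 (5%) | 0.61 (11%) |

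Under these assumptions the estimate moves a good deal, while power is low in every row.

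**The case against.** **The SAP does address prior disease.** It does, and its stated aim is the right one. The defect is an incomplete rule, not an absent one.

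**Nothing says that baseline cases are scored.** Correct. A reader might infer that every subject with nephropathy at entry is counted as an on-study case. The documents do not support that: the synopsis in the protocol speaks of nephropathy during the study, SAP 7.5.1.9 refers to post-baseline visits when summarising method of diagnosis, and whether a known case is entered again later depends on an eCRF that we do not have. What stands is that no rule prevents it.

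**The biopsy-proven count will be visible.** It will, because the table is split and all positive biopsies go into the study report. A reader might conclude that the endpoint does not measure on-treatment disease at all. That is too strong: new cases are captured, but possibly mixed with prior and unbiopsied ones in the figure that is tested.

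**Unbiopsied diagnoses simply restate viral load.** This is another tempting inference. Protocol 8.3 shows that investigators receive the viral loads and are advised to use them in management. No document gives criteria for a clinical or other diagnosis, so the dependence is possible but not established.

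**Biopsy-only would be worse.** This has force. Biopsies are not mandated, so a biopsy-only endpoint depends on whom the investigator chooses to biopsy and misses unbiopsied disease. It argues for testing both definitions, not for replacing the wider one.

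**Prevalent disease may be rare.** Entry requires transplant within a year and excludes viral load above 10³ copies/mL for more than 4 months. Protocol 1.1 puts median nephropathy onset at 42 weeks after transplant. These limit prevalent cases but do not exclude them.

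**Conclusion.** The point holds in bounded form. The tested proportion is wider than the protocol's definition, and SAP Section 9 does not say so. The plan has no new-onset requirement and no link to its own baseline nephropathy variable. Its carve-out misses subjects with a pre-study biopsy and clinical-only cases, and it conditions exclusion on post-randomisation response as judged by a committee with access to unblinded data. Followed as written, the plan can count nephropathy documented at entry, against its own stated aim.

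The size that rests on the documents alone is 12.5 points per case in an active arm and 8.3 points on pooled placebo. The diluted risk ratios of 0.40 to 0.71, against an assumed true 0.25, rest on assumed prevalence, risk and effect and show direction only. The number of affected subjects is unknown and could be zero. This is a secondary endpoint, without multiplicity control, in a study not powered for efficacy. The issue affects interpretation of the nephropathy result and not the primary safety objective.

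**What to change.** In SAP 7.5.1.9:

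1. Define a case as nephropathy first diagnosed after the first dose, in subjects without pre-existing nephropathy under 7.3.3. State whether subjects only possibly affected at baseline are treated as pre-existing. List subjects with pre-existing nephropathy, and their course, separately.
2. Make any further exclusion for suspected prior disease a blinded decision that does not use post-baseline viral load. State whether it applies to the tested proportion as well as the summary, and to numerator, denominator or both.
3. Run the logistic and Fisher analyses on the Protocol 8.4 biopsy-proven definition as well, next to the any-method count and not in place of it.

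In SAP Section 9, record the case definition and how it differs from Protocol 8.4.

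The cost is wording and one extra table, with a slightly smaller denominator and fewer events. No biopsy or visit is added. Before finalising, confirm that the eCRF captures date of first diagnosis and Banff class: the documents say that biopsy results are recorded but do not show those fields.

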7.5.2 Exploratory Endpoints

7.5.2.1 Proportion of Subjects with Presence of Anti-Drug Antibodies (ADA) at Any Time during the Study

The number and percentage of subjects with presence of anti-drug antibodies (ADA) at any post-baseline visits during the study will be summarized descriptively.

All ADA data will be listed by treatment and subject.

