- Proportion of subjects with presence of anti-drug antibodies (ADA) at any time during the study
- Presence of genotypic resistance
- Viral kinetics of BKV in plasma and urine

SAFETY ENDPOINTS:

- Physical examinations, vital signs, clinical safety laboratory parameters, 12-lead ECGs, and adverse events.

PHARMACOKINETIC ENDPOINTS:

- MAU868 serum concentrations

DISCONTINUATION OF STUDY DRUG OR STUDY PARTICIPATION:

Study drug for an individual subject must be discontinued for any of the following reasons:

- The subject withdraws consent or requests discontinuation for any reason.
- Occurrence of any medical condition or circumstance that exposes the subject to substantial risk and/or does not allow the subject to adhere to the requirements of the protocol.
- Any SAE, clinically significant adverse event, severe laboratory abnormality, intercurrent illness, or other medical condition which indicates to the Investigator or Sponsor that continued participation is not in the best interest of the subject. Specifically, study drug must be discontinued in subjects with development of a treatment-related SAE, a treatment-related AE Grade 3 or higher, or a clinically significant treatment-related laboratory abnormality Grade 3 or higher.
- Pregnancy during treatment period.
- Subject failure to comply with protocol requirements or study-related procedures.

- Subject experiences study drug related symptoms that the Investigator determines are consistent with any of the following:
 - Anaphylaxis or severe allergic reaction.
 - An infusion reaction determined to be Grade 3 or higher based on Common Terminology Criteria for Adverse Events (CTCAE) version 5.
 - Cytokine release syndrome determined to be Grade 2 or higher based on CTCAE version 5.
 - Serum sickness determined to be Grade 2 or higher based on CTCAE version 5.

Changes in BKV plasma viral load, use of rescue therapy, and/or need for change in immunosuppressive regimen for any reason should not prompt early discontinuation of therapy.

If a subject is discontinued from study drug treatment administration the subject will still be encouraged to complete follow-up visits and assessments necessary for appropriate safety follow-up.

Study participation by an individual subject must be prematurely discontinued for any of the following reasons:

- The subject withdraws consent or requests discontinuation for any reason.

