A first-in-human study explored single ascending doses of MAU868 (1, 3, 10, 30, and 100 mg/kg IV) and the serum concentration data was used to develop a PK model. The model was then used to estimate C_{trough} concentrations for a series of 3 treatment regimens. To have a treatment effect on BK viremia, MAU868 would need to curtail BKV replication in the target tissue (i.e., kidney). Based on an *in vivo* radiolabeled study in animals and PBPK modeling estimates, the antibody biodistribution coefficient in kidney is 13.7% (Shah and Betts 2013). The estimated trough levels for each treatment arm were compared directly to *in vitro*-determined antiviral activity (EC₅₀ and EC₉₀) for each BKV genotype and corrected for the assumed antibody distributions in kidney.

These data show that the planned dose regimens of MAU868 for each treatment arm provides high virus neutralizing tissue levels with kidney exposures at C_{trough} \geq 10-fold the EC₅₀ of the least susceptible BKV genotype (genotype III). Specifically, kidney exposures at C_{trough} range from 253 to 2618-fold (Cohort 1), 365 to 3775-fold (Cohort 2), and 1264 to 13,061-fold (Cohort 3) above the EC₅₀ at the end of treatment (12 weeks, range = least to most susceptible BKV genotype). Using EC₉₀ determinations, kidney exposures at C_{trough} range from 6 to 231-fold (Cohort 1), 8 to 333-fold (Cohort 2), and 28 to 1152-fold (Cohort 3) above the EC₉₀ at the end of treatment.

A 12-week treatment period was selected to ensure sustained levels of MAU868 to inhibit virus replication and promote virus clearance. The subsequent 24-week follow-up period will allow evaluation of the durability of effect and additional safety and PK observations.

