7.3.5 Day 28 (Study Drug Infusion 2)

The following procedures will be performed **prior to initiation of the study drug infusion**; see Schedule of Events ([Appendix A](#)):

- Review and record adverse events.
- Review and record concomitant medications.
- Obtain subject weight
- Collect blood (serum and plasma) and urine samples for BK viral load testing, viral resistance, immunogenicity, pharmacokinetics, hematology, clinical chemistry, and urinalysis for analysis at central laboratories.
- Perform urine or serum pregnancy test for women of childbearing potential.
- Record vital signs, including temperature, blood pressure, heart rate, respiratory rate, and oxygen saturation within approximately 30 minutes prior to the initiation of the infusion.

If the subject experienced an infusion reaction during their prior administration of study drug, future infusions should be preceded by use of premedication and decreasing the infusion rate (see [Section 6.4](#)).

The following procedures will be performed **after the initiation of the study drug infusion**; see Schedule of Events ([Appendix A](#)):

- Record vital signs, including temperature, blood pressure, heart rate, respiratory rate, and oxygen saturation approximately every 30 minutes (+/- 10 minutes) after the start of the infusion until at least 2 hours after completing the infusion. Vital signs may also be collected at any time during or after the infusion at the Investigator's discretion.
- Collect blood (serum) for pharmacokinetics within approximately 30 minutes following the completion of the infusion.
- Review and record adverse events.
- Review and record any new concomitant medications.

Study Drug Administration

Cohort 1: Study Drug Administration Day 28

The subject will receive their study drug infusion (MAU868 1350 mg or Placebo). The respective infusions will be delivered over at least 60 minutes. Following completion of the infusion (infusion bag completely emptied into the drip chamber) a 25 mL D5W flush is to infuse at the same infusion rate as the dose of IP. Start and stop times will be recorded on the eCRF.

Cohort 2: Study Drug Administration Day 28

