8.5.8 Other Assessments: Viral Resistance and Immunogenicity

To monitor for the possible development of resistance-associated variants (RAVs) to MAU868, the BKV VP1 coding region will be sequenced and translated to the corresponding amino acid sequence. The VP1 amino acid sequences from subjects will be aligned to their corresponding baseline sequences (derived from BKV detected in the urine at Baseline) and reference isolate sequences to determine if any change from-baseline or change-from-reference RAVs are present. The susceptibility of RAVs to MAU868 will be determined by cloning the subject derived VP1 gene into a BKV reference isolate vector, generating a chimeric virus for MAU868 phenotypic assessment. The EC50 and EC90 values and fold change from baseline and reference values will be reported. If the resulting chimeric virus does not replicate, the individual RAV(s) may be engineered directly into the BKV reference isolate vector through site-directed mutagenesis and

assessed for susceptibility to neutralization by MAU868. The emergence of RAV(s) conferring reduced susceptibility will be correlated to the MAU868 exposure. For subjects with confirmed RAV(s) displaying reduced MAU868 susceptibility, the persistence of the RAV(s) will be monitored for at least 6 months following the end of MAU868 therapy by periodic BKV sequencing provided the virus remains detectable in either the blood or the urine. To date, no epitope-mutant BK viruses with both a significant loss of susceptibility to MAU868 and a preservation of replicative fitness have been identified.

Details of viral resistance monitoring and detection will be described in the Virology Analysis Plan.

Immunogenicity will be evaluated using a validated ligand binding assay (ELISA or MSD) for the detection of potential anti-MAU868 antibodies.

The detailed methods for immunogenicity assessment will be described in the Bioanalytical Data Report.

Results of the viral resistance and immunogenicity samples will not be reported to the site. These samples will be analyzed, and the results reported by centralized third-party specialty labs.

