10.5 Efficacy Analysis

Efficacy objectives of this study are secondary and include:

- To assess the impact of MAU868 on BKV related outcomes including viremia, BKV nephropathy, graft function and rejection among renal transplant patients with BK viremia

- To assess the pharmacokinetics of MAU868

Exploratory:

- To investigate the potential immunogenicity of MAU868
- To investigate genotypic resistance

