3. During the follow-up period, if the subject cannot be seen on the precise protocol-defined study day, the acceptable visit window is +/-10 days.
4. Study Day 1 is the calendar day on which the first dose of study drug is administered. Subsequent study days are based on calendar days.
5. The information necessary for determining the KDPI includes *donor* age, height, weight, ethnicity, history of hypertension, history of diabetes mellitus, cause of death, serum creatinine, hepatitis C serostatus, and whether donation occurred after circulatory death.
6. Record any and all immunosuppressive medication from induction to randomization as well as any other medications taken during the 10 days prior to randomization.
7. Randomization should occur as soon as possible after confirmation of qualifying viremia but not more than 10 days after the qualifying sample was collected. Dosing of study drug should occur as soon as possible after randomization.
8. In the event that a subject requires hemodialysis, plasmapheresis, or immunoabsorption treatments; if <15 days since last MAU868/placebo treatment another dose will be given as soon as possible, and the next scheduled monthly dose skipped. Regular dosing will occur the following month. If the last dose was 15 days or greater no interim dose will be administered and the regular monthly scheduled will be followed. No subject will receive more than 4 doses.
9. A sufficient amount of urine should be collected at each assessment to accommodate three tests; one for BKV DNA PCR, one for possible genotypic resistance testing and a back up sample. Refer to the study's Laboratory Manual for volume requirements.
10. On Study Day 1 collect samples for BKV PCR, antidrug antibodies, and safety labs prior to administration of first dose of MAU868. Refer to the study's Laboratory Manual for collection requirements.
11. After screening, plasma samples should be collected and sent to the central laboratory at each assessment for BKV DNA PCR, possible genotypic resistance testing and a backup sample. During screening, only BKV PCR is required and may be performed by the laboratory used by the site for usual clinical care, or sent to the central lab for testing. Refer to the study's Laboratory Manual for volume requirements.
12. In the event subject undergoes hemodialysis, plasmapheresis, or immunoabsorption treatment, a PK sample should be collected prior to and following the respective treatment.

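### The ADA summary counts any post-baseline positive without using the Day 1 result, so pre-existing reactivity is mixed with ADA arising on treatment; some negatives may also be uninterpretable, depending on the assay's drug tolerance

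*SAP*

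**What the plan says.** Protocol 10.5 gives the exploratory objective: "To investigate the potential immunogenicity of MAU868". The synopsis states the endpoint as "Proportion of subjects with presence of anti-drug antibodies (ADA) at any time during the study".

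SAP 7.5.2.1 turns this into a single summary, the number and percentage with "presence of anti-drug antibodies (ADA) at any post-baseline visits during the study will be summarized descriptively", and adds that "All ADA data will be listed by treatment and subject". It sets no condition on Day 1 status, defines no treatment-induced or treatment-boosted class, and does not refer to drug level. SAP section 9, which lists changes from the protocol, adds no such rule.

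The data for a finer rule are collected:

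- Protocol Appendix A, footnote 10: "On Study Day 1 collect samples for BKV PCR, antidrug antibodies, and safety labs prior to administration of first dose of MAU868".
- The schedule of events has later ADA samples on Days 28, 56, 84, 112, 140 and 252 (or early termination), with a PK sample at each of those visits. On Day 28, for example, the pre-infusion draw covers "immunogenicity, pharmacokinetics, hematology, clinical chemistry, and urinalysis for analysis at central laboratories".

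Protocol 8.5.8 describes the method as a "validated ligand binding assay (ELISA or MSD) for the detection of potential anti-MAU868 antibodies" and leaves the details to a Bioanalytical Data Report. It states no drug tolerance, titre step or confirmatory tier.

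**The concern.** Immunogenicity of a drug means antibody that the drug induced or boosted. A count of post-baseline positives equals that only if nobody is reactive before dosing. Where someone is, the percentage for that arm carries background reactivity, and the reader of the table cannot tell how much.

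The documents use baseline in comparable places. Protocol 8.5.8 aligns each subject's VP1 sequences to that subject's baseline sequence. SAP 7.5.1.9 removes certain biopsy-proven nephropathy cases from the summary because they probably predate entry. ADA, whose baseline is measured directly, gets no such step.

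The second question is what a negative means. A ligand-binding assay can miss antibody that is bound to circulating drug. If on-treatment levels exceed what the assay tolerates, a negative drawn at that level says little. The rule as written nevertheless leaves such a subject among those without ADA.

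**Working it through.** The documents give no ADA rate, so there is no planned figure to reproduce. The check sizes each part.

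**1. Weight of one subject.** The planned groups are 8 active per cohort, 24 active in all and 12 pooled placebo (SAP section 3). One subject is 100/8 = 12.5 points in an arm, 100/24 = 4.2 points in pooled active, and 100/12 = 8.3 points in pooled placebo.

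**2. Chance of at least one pre-existing reactor.** Prevalence p is not in the documents; 1% to 10% is assumed. The chance is 1 − (1 − p)^n.

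| p | n = 8 | n = 12 | n = 24 |
|---|---|---|---|
| 1% | 8% | 11% | 21% |
| 2% | 15% | 21% | 38% |
| 5% | 34% | 46% | 71% |
| 10% | 57% | 72% | 92% |

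Such a subject distorts the count only if also positive at some later visit.

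**3. Serum level at week 12.** Protocol 1.6 gives kidney trough multiples of "253 to 2618-fold (Cohort 1), 365 to 3775-fold (Cohort 2), and 1264 to 13,061-fold (Cohort 3) above the EC" (the quoted run stops before the subscript 50). The lower multiples refer to genotype III, with an EC50 of 0.093 ug/mL, and the kidney coefficient is 13.7%. Serum trough = multiple × EC50 / 0.137.

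- Cohort 1: 253 × 0.093 / 0.137 = 171.7 ug/mL
- Cohort 2: 365 × 0.093 / 0.137 = 247.8 ug/mL
- Cohort 3: 1264 × 0.093 / 0.137 = 858.0 ug/mL

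The upper multiples with the genotype I EC50 of 0.009 give 172.0, 248.0 and 858.0, so the protocol's figures agree with each other.

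**4. Serum level at Day 252.** The half-life is not stated; 21 to 35 days is assumed. Taking the week-12 trough as the Day 112 level, Day 252 level = trough × 2^(−140 / half-life).

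| Half-life | Cohort 1 | Cohort 2 | Cohort 3 |
|---|---|---|---|
| 21 days | 1.7 | 2.4 | 8.5 |
| 28 days | 5.4 | 7.7 | 26.8 |
| 35 days | 10.7 | 15.5 | 53.6 |

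The half-life can be roughly checked from the protocol's own numbers with a one-compartment model, where r is the fraction left after 28 days and half-life = 28 ln 2 / (−ln r). The Cohort 3 trough over the single-dose Day 28 mean of 509.8 ug/mL (Protocol 1.4.2) gives 25.4 days if the trough follows three doses and 22.7 if it follows four. The Cohort 2 to Cohort 1 ratio, 365/253, gives 22.4 and 42.4 days on the same two readings. Three of the four lie in the assumed range. At 42 days the Day 252 levels would be about 17, 25 and 85 ug/mL.

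**5. Does this mask ADA?** Drug tolerance is unknown, so take 10 to 100 ug/mL as an illustrative assumption. At 100, every arm is within tolerance on Day 252 across the 21 to 35 day range. At 10, every arm is within it with a 21-day half-life and none is with 35 days (10.7, 15.5 and 53.6 all exceed 10). The answer depends on quantities that the documents do not supply.

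**The case against.** The SAP reports presence of ADA and never calls it drug-induced. The Day 1 result is not discarded, because it appears in the listing, and with about 36 subjects a Day 1 positive would be easy to spot. Pooled placebo shows background reactivity. The endpoint is exploratory and descriptive. Assay methods are deferred to a Bioanalytical Data Report, and PK to a separate plan run by another vendor, so use of drug levels could be specified there.

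Most of this is fair and limits the point. It does not repair the reported percentage. A listing leaves each reader to recompute the rate, and 12 placebo subjects are a weak check: at 5% prevalence they would contain no reactor with probability 0.95^12 = 54%. A methods report on the assay would also not put a classification rule into the SAP.

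A reader might go further and infer that a 0% rate could mean only that drug masked the assay. The documents do not support that. The rule takes any post-baseline visit, including Day 252, where the estimated levels fall within much of the illustrative tolerance range. Nor would every on-treatment trough exceed that range. For 20 mg/kg (1350 mg at 67.5 kg), the first Cohort 1 trough is about 0.2 × 509.8 = 102 ug/mL, or about 116 as the midpoint of the 10 and 30 mg/kg means (59.9 and 171.3), so individual values below 100 are likely.

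A reader might also infer that links from ADA to infusion reactions or to response would be wrong. SAP 7.4 and 7.5 plan no such analysis. Protocol 10.8 lists ADA among the safety summaries, but the SAP supersedes the protocol on analysis, and SAP 7.4 has no ADA table.

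**Conclusion.** The first part holds on the text alone: the planned ADA percentage does not use the Day 1 result and therefore does not isolate ADA arising on treatment, which is what the objective asks about. One misclassified subject is worth 12.5 points in an active arm of 8. How likely that is depends on an assumed prevalence; at 2% to 5%, the chance of at least one pre-existing reactor among 24 active subjects is 38% to 71%.

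The second part is a conditional risk. Levels of about 170 to 860 ug/mL at week 12 follow from the protocol's figures. The 2 to 54 ug/mL at Day 252 rests on the assumed half-life and on treating the week-12 trough as the Day 112 level. Whether any negative is uninterpretable cannot be decided without the assay's drug tolerance.

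No hypothesis test, alpha or sample size is affected. What changes is the meaning of one exploratory percentage.

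**What to change.** In SAP 7.5.2.1, report by arm:

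- Day 1 ADA prevalence.
- Treatment-emergent ADA: negative on Day 1 and positive later, or positive on Day 1 with a titre rise above the assay's validated fold, if titres are reported. The denominator is subjects with a Day 1 result and at least one post-baseline result.
- The any-post-baseline-positive count, as a supplement.

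Once the drug tolerance is available from the assay validation report, state it in the SAP. Classify a never-positive subject as inconclusive if no post-dose ADA sample has a same-visit MAU868 level within that tolerance, and as negative otherwise.

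The cost is SAP wording, one table and a merge of ADA results with PK results already planned; no new samples are needed. The second step needs the tolerance figure and a data transfer from the PK vendor. The downside is that some subjects may move from negative to inconclusive.
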